2.6 Randomization

Patients were randomized using the Research Randomizer tool (<https://www.randomizer.org/>) into three groups: VR, placebo-video, and control.

3. Interventions and Data Collection

3.1 Tools

Patient Information Form: Sociodemographic and clinical data.

Visual Analog Scale-Anxiety (VAS-A): Scores from 0 (no anxiety) to 10 (maximum anxiety).

Smart Bracelet (Xiaomi Mi Band 5): Measures heart rate variability-based stress (1100 scale).

3.2 Procedures

Evaluation 1 (T1):

- Conducted in the patient's room in the morning.
- Informed consent obtained; forms and baseline anxiety/stress measurements completed.

Evaluation 2 (T2):

- Conducted 10–15 minutes after intervention or rest period

Virtual Reality Group:

- Watched a 2-hour 4K virtual forest video (<https://www.youtube.com/watch?v=uEMmpJgaXvo>).
- Used Zore G04E VR Shinecon headset with headphones and disposable eye covers.
- The researcher observed for any adverse effects.

Placebo-Video Group:

Watched the same video on a smartphone using disposable headphones

Control Group

No intervention; second evaluation conducted after ~15 minutes of rest.

4. Ethical Considerations

Approval was obtained from the Trakya University Ethics Committee (TÜTF-GOBAEK 2022/240) and the hospital administration (E-51088030-100-317619). All participants provided verbal and written informed consent. The study adhered to the Helsinki Declaration and CONSORT guidelines

5. Statistical Analysis Plan

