2.4 Participants

Inclusion Criteria:

- Adults aged ≥ 18 years
- Undergoing elective abdominal surgery (e.g., appendectomy, hernia, gallbladder/pancreas surgery)
- Awaiting transfer to the operating room in the morning
- Able to communicate and provide informed consent

Exclusion Criteria:

- Abdominal cancer surgery
- Emergency or unplanned surgery
- Isolation status
- Visual/auditory impairments
- Neurological disorders (e.g., vertigo)

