2.5 Sample Size

The sample size was calculated based on the study by Mosso et al. (2009) using G*Power 3.1.9.7 software. With an effect size of $d=0.920$, $\alpha=0.05$, and $\text{power}=0.95$, a total of 96 patients were required (32 in each group).

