5.2. Descriptive Statistics

- Continuous variables (e.g., age, anxiety, stress): Mean, SD, median, min, max
- Categorical variables (e.g., gender, education, chronic diseases): Frequency and percentage

5.3.Normality Testing

Shapiro-Wilk test for all continuous variables

5.4.Inferential Statistics:

-Between-Group Comparisons:

Kruskal-Wallis H Test for comparing continuous variables across the three groups

Mann-Whitney U Test with Bonferroni correction for post-hoc pairwise comparisons

-Within-Group Comparisons (T1 vs. T2):

Wilcoxon Signed Ranks Test

-Categorical Variables:

Pearson Chi-Square Test

5.5.Statistical Significance

Significance level set at $p < 0.05$

Confidence interval: 95%

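### Adverse-effect observation is planned for the VR arm only, with no stated recording method, so the plan cannot support a comparative statement on headset-related symptoms

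*Combined protocol and SAP*

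**What the plan says.** Section 2.6 randomises patients "into three groups: VR, placebo-video, and control". Section 3.2 then describes each arm, and only the VR description mentions adverse effects: "The researcher observed for any adverse effects". The placebo-video arm is described in one line: "Watched the same video on a smartphone using disposable headphones". So is the control arm: "No intervention; second evaluation conducted after ~15 minutes of rest".

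Section 3.1 lists three tools: the Patient Information Form, the VAS-A and the smart bracelet. None is described as recording symptoms or adverse effects. There is no list of expected symptoms, no grading, no time window and no recording form.

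In section 5.2 the continuous variables are given as "Continuous variables (e.g., age, anxiety, stress): Mean, SD, median, min, max". The categorical line gives gender, education and chronic diseases as examples. Section 5.4 adds a general Pearson chi-square test for categorical variables. No adverse-effect variable, table or comparison is named.

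Among the exclusions in section 2.4 is "Neurological disorders (e.g., vertigo". That is consistent with headset symptoms having been foreseen, but the documents do not give it as the reason.

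**The concern.** When one randomised arm is watched for harm and the plan is silent on the others, the count from the watched arm has no reference. Patients waiting for abdominal surgery may feel dizzy, nauseated or have a headache without any headset. Such events would be counted under VR with nothing to show how much is background. Symptoms that are felt but neither shown nor volunteered could be missed if the observation does not include asking, and the plan does not say whether it does.

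The design already contains a suitable comparator. The placebo-video arm watches the same video without the headset, so the VR minus placebo-video contrast is the one that bears on the headset. The plan does not use it for symptoms. At stake is any statement in the report on the tolerability of VR relative to the other arms. The anxiety comparison is not at stake.

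**Working it through.** **1. The plan's own figure.** Section 2.5 states "With an effect size of $d=0.920", α = 0.05 and power 0.95. A two-sided two-sample t-test (noncentral t) with these inputs needs 32 per arm (power 0.952), and 3 × 32 = 96. This reproduces "a total of 96 patients were required (32 in each group". That figure concerns anxiety and is not disputed here. It supplies n = 32 per arm for the steps below.

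**2. What the plan as written can estimate.** The documents plan adverse-effect information for at most 32 VR patients and for no comparator, so no between-arm difference can be estimated. For the single arm, exact (Clopper-Pearson) 95% limits are:
- 0/32: upper limit = 1 − 0.025^(1/32) = 10.9%.
- 6/32 (18.8%), taken as an illustration: 7.2% to 36.4%, with no way to tell how much is background.

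**3. How much background could matter.** The documents give no symptom rate, so a range of 5% to 15% unrelated to VR is assumed. The calculation also assumes that every such symptom is noticed and recorded.
- Expected VR patients with a symptom and no VR effect: 32 × 0.05 = 1.6 to 32 × 0.15 = 4.8.
- Chance of at least one: 1 − 0.95^32 = 0.806 to 1 − 0.85^32 = 0.994.

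Under these assumptions a few events in the VR arm would be expected with a harmless headset. The figures follow from the chosen rates and measure nothing about this trial.

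**4. What equal recording would give.** With 32 per arm and assumed rates of 20% (VR) and 10% (placebo-video), the 95% half-width of the risk difference by the normal approximation is

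1.96 × √(0.20 × 0.80/32 + 0.10 × 0.90/32) = 1.96 × √0.0078125 = 0.173,

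or about 17 percentage points. Power at two-sided 0.05 for 20% versus 10% is 0.20, and 80% power would need 199 per arm. With 32 per arm, 80% power is reached only at about:

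| Assumed placebo-video rate | VR rate needed | Difference (points) |
|---|---|---|
| 5% | 32% | 27 |
| 10% | 40% | 30 |
| 20% | 54% | 34 |

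The contrast would be an estimate with a wide interval, not a test.

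**5. Which comparator.** Section 3.2 puts T2 10 to 15 minutes after the intervention or rest. If the 2-hour video is watched in full, T1 to T2 spans at least 120 + 10 = 130 minutes in the VR and placebo-video arms, against about 15 minutes of rest in the control arm. New symptoms have far less time to appear in controls, so VR minus placebo-video is the usable contrast.

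**The case against.** The strongest reply is that section 2.1 sets one aim, the effect on preoperative anxiety. There is no safety objective, the sentence in section 3.2 can be read as ordinary monitoring of patients under a headset, and no harm comparison is announced. This stands as a limit on the point: the anxiety analysis is untouched, and the plan makes no misleading comparison of its own.

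Second, the protocol is brief, and silence is not proof of absence. A reader might infer that the observation was visual only, that nobody looked in the other arms, or that symptoms after headset removal had no chance of being recorded. The documents support none of these. Observing for adverse effects does not exclude asking, the sentence sets no time limit, and the content of T2 is not itemised. A reader might also set a VR count against zero in the other arms. Not recorded is not 0/32, and the plan does not treat it so.

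Third, the general categorical lines in sections 5.2 and 5.4 could accommodate a yes/no event, and the Patient Information Form covers clinical data. That is so once the event is recorded in every arm. It does not help while the only planned ascertainment is in one arm.

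Fourth, the remedy has limits. Precision is low, the control window is not comparable, and prompting may not raise reports equally, because patients know whether they wear a headset. All of this stands. It is why the comparison should be labelled descriptive and rest on VR against placebo-video.

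**Conclusion.** The point holds in a limited form. Adverse-effect observation is planned for the VR arm only, its recording method is not stated, and neither the tools nor the analysis plan names a symptom instrument or adverse-effect variable. Followed as written, the trial gives an uncontrolled count from at most 32 patients, and no later analysis can turn that into a statement about headset symptoms relative to ordinary preoperative ones. Even a count of zero leaves rates of up to 10.9% compatible with the data.

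It is a point that should be addressed, and it does not threaten the main result. It rests on the text as written; if the other arms were in fact observed in the same way, saying so would answer much of it. The size of any bias cannot be computed from the documents, because they give no symptom rates.

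**What to change.** - **Section 3.2:** move adverse-effect recording out of the VR list and into Evaluations 1 and 2 for all three arms. Ask every patient the same short yes/no symptom questions (for example dizziness or vertigo, nausea, headache, eye discomfort), after the VAS-A so that they cannot influence it. In the VR and placebo-video arms, record whether viewing ended early and why.
- **Section 3.1:** add these questions to the Patient Information Form.
- **Section 5:** add, by arm, the number and percentage with a new symptom (absent at T1, present at T2) and, for the two viewing arms, with early stopping. Add the VR minus placebo-video difference with an exact 95% CI, naming the method and labelling it descriptive. Tabulate the control arm, but do not use it as the main comparator.

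**Cost:** about one minute per evaluation at two existing time points, one form section and one table, with no extra staff or patients. Prompting will produce some additional reports, possibly unequally between arms, and the interval will be wide.

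**If data collection is closed:** section 2.3 gives a study period ending in December 2024, so symptoms not collected may be unrecoverable. In that case, state that adverse effects were observed in the VR arm only (or describe what was done elsewhere), tabulate what was recorded, and make no comparative safety claim.

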5.1. Software

Data analysis was performed using IBM SPSS Statistics for Windows, Version 28.0

5.2. Descriptive Statistics

- Continuous variables (e.g., age, anxiety, stress): Mean, SD, median, min, max
- Categorical variables (e.g., gender, education, chronic diseases): Frequency and percentage

5.3.Normality Testing

Shapiro-Wilk test for all continuous variables

5.4.Inferential Statistics:

-Between-Group Comparisons:

Kruskal-Wallis H Test for comparing continuous variables across the three groups

Mann-Whitney U Test with Bonferroni correction for post-hoc pairwise comparisons

-Within-Group Comparisons (T1 vs. T2):

Wilcoxon Signed Ranks Test

-Categorical Variables:

Pearson Chi-Square Test

5.5.Statistical Significance

Significance level set at $p < 0.05$

Confidence interval: 95%

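### Section 5.4 compares the arms on anxiety and stress by unadjusted rank tests that ignore the T1 values already collected, and it does not name the time point tested

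*Combined protocol and SAP*

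**What the plan says.** Section 3.2 provides a baseline for both outcomes. At T1 the plan has "Informed consent obtained; forms and baseline anxiety/stress measurements completed", and a second evaluation follows at T2.

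Section 5.2 lists the outcomes among the variables to be summarised: "Continuous variables (e.g., age, anxiety, stress): Mean, SD, median, min, max".

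Section 5.4 gives two between-arm procedures: "Kruskal-Wallis H Test for comparing continuous variables across the three groups" and "Mann-Whitney U Test with Bonferroni correction for post-hoc pairwise comparisons". Neither line names an outcome, a time point or a covariate. T1 and T2 appear together only under "Within-Group Comparisons (T1 vs. T2)", where the test is the Wilcoxon signed ranks test, applied inside each arm.

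Section 5.5 adds "Confidence interval: 95" percent, without saying which estimate the interval belongs to.

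**The concern.** The trial's aim is a comparison between arms. A baseline value of the same outcome is usually the covariate that explains most of the variation in the final value, and here it is measured in every patient anyway. Kruskal-Wallis and Mann-Whitney tests cannot take a covariate, so that information goes unused where the arms are compared. The within-arm Wilcoxon tests do use it, but they do not compare arms.

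The unnamed time point is a smaller, related gap. A reader cannot tell from section 5.4 which result answers the aim. The form matters for power: the same rank test applied to T2 or to the change from T1 performs quite differently, depending on how strongly T1 and T2 are correlated.

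**Working it through.** **Inputs from the documents.** d=0.920, alpha 0.05, power 0.95, 32 per group and 96 in total (section 2.5); three arms (section 2.6); VAS-A scored 0 to 10 (section 3.1); Bonferroni correction (section 5.4).

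**Assumptions.** The documents give no T1-T2 correlation r, so 0.1, 0.3, 0.5 and 0.7 are shown. Section 2.5 does not say whether d refers to T2 or to change; it is taken as a T2 difference. SDs at T1 and T2 are taken as equal. Three pairwise comparisons give alpha 0.05/3 = 0.0167.

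**Step 1: the plan's own figure.** Two-sided two-sample t test, noncentrality d·√(n/2) = 0.92 × √16 = 3.68, 62 df. Power is 0.952 with 32 per arm and 0.946 with 31, so 32 per group and 3 × 32 = 96 reproduce. The sample size is not in question here. At alpha 0.0167 the same comparison has power 0.885.

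**Step 2: normal theory at alpha 0.0167.** The effective d is:
- T2 alone: d
- change: d/√(2(1−r))
- ANCOVA: d/√(1−r²)

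For example, at r=0.5 the ANCOVA value is 0.92/√0.75 = 1.062. At r=0.3 the change value is 0.92/√1.4 = 0.778.

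| r | T2 alone | Change | ANCOVA |
|---|---|---|---|
| 0.1 | 0.885 | 0.612 | 0.888 |
| 0.3 | 0.885 | 0.740 | 0.915 |
| 0.5 | 0.885 | 0.885 | 0.960 |
| 0.7 | 0.885 | 0.988 | 0.996 |

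**Step 3: the planned rank test against its adjusted counterpart.** Simulated two-arm trials, 20,000 per cell (Monte Carlo SE at most 0.0035), with integer scores from a bivariate normal with mean 5 and SD 2, rounded and clipped to 0-10. The mean and SD are assumptions. Quade's test regresses pooled T2 ranks on T1 ranks and compares the residuals between arms.

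| r | Mann-Whitney, T2 | Quade | Gain | Mann-Whitney, change |
|---|---|---|---|---|
| 0.1 | 0.854 | 0.854 | 0.000 | 0.564 |
| 0.3 | 0.860 | 0.889 | 0.029 | 0.696 |
| 0.5 | 0.857 | 0.937 | 0.080 | 0.843 |
| 0.7 | 0.858 | 0.987 | 0.129 | 0.974 |

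Under no effect, all of these tests reject in 0.014 to 0.018 of trials, close to the nominal 0.0167.

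**Step 4: precision of the estimate.** Mean half-width of the 95% interval in VAS points, same symmetric scores: 0.98 unadjusted; 0.98, 0.94, 0.86 and 0.72 with ANCOVA at r = 0.1, 0.3, 0.5 and 0.7.

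**Step 5: worst case for the unnamed form.** If the analyst could take whichever of T2 or change gave significance, the Kruskal-Wallis error would be about 0.09 instead of 0.05. A single pairwise error would be 0.028 to 0.032 instead of 0.0167, still below 0.05.

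**The case against.** **The planned tests are sound.** Rank tests are a legitimate choice on a 0-10 scale, and randomisation protects their error rate. On the T2 assumption they have power of about 0.86. The gain from adjustment is nil at r=0.1 and small at r=0.3, and the documents give no r. All of this stands, and it is why the point concerns efficiency only.

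**The time point is fairly clear.** No change score is defined anywhere. The natural reading is that each measured variable is compared across arms at each time point, with the T1-T2 contrast left to Wilcoxon. This largely stands. It makes the missing time point a one-sentence clarification, but it still leaves no T1-adjusted comparison and does not say which test decides.

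**A stronger inference to avoid.** A reader might infer that the plan lets the sponsor choose between T2 and change, and so inflates the type I error. The documents do not support that. The plan never offers change as an alternative, nothing shows that a choice was made on results, and the 0.09 is a worst case for the omnibus test only. Nor do they support reading the missing covariate as a source of bias.

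**The T1-T2 interval may differ by arm.** Section 3.2 has the VR arm down as "Watched a 2-hour 4K virtual forest video" and the control arm as "No intervention; second evaluation conducted after ~15 minutes of rest", so r might differ by arm. With r of 0.3 in one arm and 0.7 in the other, null rejection for Quade and ANCOVA stayed at 0.016 to 0.017 and ANCOVA 95% interval coverage at 0.945 to 0.952. The unequal interval is a design question in its own right, and baseline adjustment does not remove it.

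**Conclusion.** The point holds as a cheap improvement, not as an error. Section 5.4 leaves a collected baseline out of every between-arm comparison and does not name the time point. The power gain runs from nothing at r=0.1 to about 0.13 at r=0.7, starting from about 0.86. It rests on d=0.92 being a T2 difference, 32 analysed per arm, three Bonferroni comparisons and roughly symmetric scores. If d instead referred to change, the ordering of T2 and change would differ.

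The lack of any r in the documents favours adjustment: change scores would lose a great deal at low r, whereas in the symmetric simulations the adjusted rank test is at least as powerful as either unadjusted form at every r shown. Confidence is medium, because the size depends on a correlation that only the trial's data can supply.

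**What to change.** **If the data are not yet analysed.**
- State in section 5.4 that T2 VAS-A, and separately T2 stress, is the variable compared between arms.
- Make one T1-adjusted test decide for each: a three-arm Quade rank ANCOVA with T1 as covariate, then pairwise Quade tests at the Bonferroni level.
- Report ANCOVA-adjusted mean differences as the estimate, with intervals at 1 − 0.05/3 = 98.3% to match the pairwise tests. Alternatively, give 95% intervals labelled as unadjusted for multiplicity.
- Keep Kruskal-Wallis and Mann-Whitney on T2 as supportive.

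**If the data are already analysed**, as the past tense of sections 2.3 and 5.1 suggests, keep the planned tests as the main result, state which time point they used, and report the adjusted analysis beside them as added post hoc.

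**Cost.** No new data: a few sentences in section 5.4, plus ranking, regression and ANCOVA commands in the software already named. The downsides are little gain if r is near 0.1, linearity and common-slope assumptions for ANCOVA on a bounded scale, and the fact that Quade's test gives no estimate in VAS points, which is why ANCOVA accompanies it.

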2.1 Aim

This study aimed to evaluate the effectiveness of virtual reality (VR) distraction in alleviating preoperative anxiety among patients scheduled for abdominal surgery

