2.2 Design

This is a double-blinded (blinded to data collection and data analysis) randomized controlled trial conducted in accordance with the Consolidated Standards of Reporting Trials (CONSORT) guidelines. The study protocol is registered at ClinicalTrials.gov (ID: NCT05718661).

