2.3 Study Setting and Period

The study was conducted between December 1, 2022, and December 20, 2024, at the General Surgery Service of a university hospital in the Trakya region, Edirne, Türkiye. The hospital serves as a referral center and contributes to medical and health sciences education.

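### VAS-A and bracelet stress are tested unranked and without T1 adjustment; the error inflation for a VR claim is modest, but a T1-adjusted between-arm VAS-A analysis should carry the conclusion

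*Combined protocol and SAP*

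**What the plan says.** The aim in section 2.1 concerns "alleviating preoperative anxiety among patients scheduled for abdominal surgery" and does not mention stress. Section 3.1 lists two outcome instruments: VAS-A (0 to 10) and a wrist-worn device giving a stress score. Section 3.2 has both measured at T1, with a second evaluation at T2.

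Section 5.2 puts the two side by side: "Continuous variables (e.g., age, anxiety, stress". Section 5.4 then prescribes the "Kruskal-Wallis H Test for comparing continuous variables across the three groups", followed by the "Mann-Whitney U Test with Bonferroni correction for post-hoc pairwise comparisons". A separate item, "Within-Group Comparisons (T1 vs. T2"), assigns the Wilcoxon signed-rank test and is the only place in the analysis plan that names T1. Section 5.5 sets 0.05 as the significance level.

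The plan does not call either outcome primary or secondary. It does not say whether the Kruskal-Wallis test uses T2 scores or changes from T1, and it does not adjust for T1. Section 2.5 states that "a total of 96 patients were required (32 in each group") but not which outcome its effect size describes. Section 2.2 adds that "The study protocol is registered at ClinicalTrials.gov", without reporting any ranking held there.

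**The concern.** There are two gaps.

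First, Bonferroni deals with three arms but not with two outcomes. Suppose stress were significant and VAS-A were not. The plan does not say whether that would count as evidence that VR works, so an anxiety trial could be reported as positive on a different measure, with two chances at 0.05.

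Second, T1 enters only through comparisons inside each arm. A significant change in the VR arm and a non-significant one in the control arm is not a comparison of the two, and randomization does not protect it. Meanwhile the between-arm comparison, which does answer the question, makes no stated use of T1 and may give up precision that the data already contain.

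**Working it through.** **1. The plan's own figure.** The inputs are d = 0.920, alpha 0.05 and power 0.95 (section 2.5). The normal approximation for two groups, two-sided, is n = 2(1.960 + 1.645)² / 0.920² = 2 × 12.996 / 0.8464 = 30.7, so 31 per group. The exact two-sided t-test gives 32 (power 0.952). The stated 32 per group is therefore reproduced as one two-arm comparison on one outcome at 0.05. It does not show which outcome that is.

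**2. Two global tests, independent outcomes.** 1 − (1 − 0.05)² = 1 − 0.9025 = 9.75%.

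**3. Correlated outcomes and the plan's full sequence.** The documents give no correlation between VAS-A and stress, so 0 to 0.7 is assumed. The simulation used 3 × 32 patients, normal data, no true effect, Kruskal-Wallis at 0.05, then Mann-Whitney pairs at 0.05/3 counted only after a significant global test. Ranges show the spread between repeated runs.

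| False result on either outcome | Correlation 0 | Correlation 0.7 | One outcome only |
|---|---|---|---|
| Significant global test | 9.5-9.6% | 8.2-8.6% | 4.8-5.0% |
| Any Bonferroni pair | 7.6-7.7% | 6.6-7.0% | 3.8-4.0% |
| A pair involving VR, either direction | 5.3-5.4% | 4.8-4.9% | about 3% |
| A pair in VR's favour | 2.5-2.9% | 2.4-2.5% | about 1.4% |

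With integer, tied scores the first row is 9.5% and 8.1%. At an extreme correlation of 0.9 it is about 7%. Stress is falsely significant on the global test while VAS-A is not in 4.6-4.7% at correlation 0 and 3.4-3.6% at 0.7. Ranking removes that part.

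**4. What T1 adjustment would gain.** Adjusting T2 for T1 with T1-T2 correlation r multiplies the residual variance by about 1 − r². For r = 0.3, 0.5 and 0.7 this is 0.91, 0.75 and 0.51. The documents give no r, so these values are assumed. The simulation compared rank ANCOVA (Quade's method) with Kruskal-Wallis on T2, with VR alone better by the stated amount:

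| | r = 0.3 | r = 0.5 | r = 0.7 |
|---|---|---|---|
| Size, rank ANCOVA | 0.052 | 0.050 | 0.049 |
| Size, Kruskal-Wallis | 0.048 | 0.049 | 0.048 |
| Power at 0.5 SD, rank ANCOVA | 0.53 | 0.60 | 0.77 |
| Power at 0.5 SD, Kruskal-Wallis | 0.49 | 0.49 | 0.49 |
| Power at 0.92 SD, rank ANCOVA | 0.975 | 0.990 | 0.999 |
| Power at 0.92 SD, Kruskal-Wallis | 0.964 | 0.963 | 0.962 |

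If the plan intends change scores instead, their variance relative to T2 alone is 2(1 − r) = 1.4, 1.0 and 0.6 at the same r. Each exceeds 1 − r², so adjustment remains the more precise choice.

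**5. Within-arm tests.** These are outside all the rates in step 3. They test change inside one arm, so no two of them together estimate a difference between arms.

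**The case against.** The strongest reply is that 8-10% measures the wrong event. A significant three-arm test may come from placebo-video against control, or from VR doing worse. The plan goes on to Bonferroni pairs, and for a claim about VR the rate is then about 5% two-sided. This stands. A reader might infer from the missing ranking that the trial has an 8-10% chance of falsely declaring VR effective; the plan's own sequence does not support that.

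It can also be said that the aim names anxiety, that VAS-A is the only anxiety scale, and that the registration may already rank the outcomes. This largely stands. If VAS-A alone decides, the global rate is about 5% and what is missing is a label. A reader might go further and infer that no primary outcome was ever fixed, or that the sponsor means to argue from stress alone or from within-arm changes. The documents show neither. They only fail to exclude such uses.

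Finally, rank ANCOVA does nothing for multiplicity, and Kruskal-Wallis holds its size. Both points are correct. The adjustment is proposed for precision, and the gain is small at the effect size used for planning, where power is already about 0.96.

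**Conclusion.** The point holds in a limited form, as a minor to moderate one. The text leaves two outcomes unranked, corrects only across arms, and gives T1 no stated role in the between-arm comparison.

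For a VR claim that follows the plan's steps, allowing either outcome to count raises the chance of a false pair in VR's favour from about 1.4% to about 2.5%, and of any false pair involving VR from about 3% to about 5%. These figures assume no true effect, normal data, 32 per arm and a correlation of 0 to 0.7 between outcomes. They apply only if a stress result could stand in for anxiety, which the plan neither proposes nor rules out.

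The more practical loss is precision. At a 0.5 SD benefit of VR alone, power is 0.49 without T1 and about 0.53 to 0.77 with it, for an assumed T1-T2 correlation of 0.3 to 0.7.

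**What to change.** In sections 5.4 and 5.5:

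1. Make the effectiveness analysis one three-arm comparison of T2 VAS-A adjusted for T1, for example by rank ANCOVA. Follow it with the three pairs at 0.05/3, using the same T1 adjustment.
2. State that the effectiveness conclusion rests on that between-arm VAS-A result, that bracelet stress is supportive, and that within-arm changes are descriptive. Check this against the registration. If the registration ranks the outcomes differently, follow and report the registered ranking. If it makes both primary, testing each at 0.025 would keep the false global rate at 4.6% (correlation 0) to 4.2% (correlation 0.7).
3. Date the ordering and the analysis method, and disclose as post hoc anything set after data collection or analysis. Section 2.3 says "The study was conducted between December 1, 2022, and December 20, 2024", and section 5.1 describes the analysis in the past tense. A ranking set now therefore improves disclosure and interpretation but cannot restore prespecified 5% control.

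The cost is that a stress-only result can no longer be claimed as confirmatory. The analysis gains a ranking and a regression step. No new patients or measurements are needed, because T1 and T2 evaluations are already part of the procedures.

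### Pairs are tested at 0.0167 although the trial was sized at 0.05; with three arms, a written Kruskal-Wallis gate would recover most of the lost power

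*Combined protocol and SAP*

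**What the plan says.** Section 2.6 randomizes patients "into three groups: VR, placebo-video, and control". Section 5.4 plans a "Kruskal-Wallis H Test for comparing continuous variables across the three groups", followed by "Mann-Whitney U Test with Bonferroni correction for post-hoc pairwise comparisons". Three arms make three pairs, so the per-pair level is 0.05/3 = 0.0167. Section 5.5 sets the overall level at 0.05.

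The plan does not say that the pairwise tests depend on a significant Kruskal-Wallis result. The term post-hoc suggests this, but no rule is written.

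Section 2.5 gives d = 0.920, alpha 0.05 and power 0.95, and concludes that "a total of 96 patients were required (32 in each group". It does not say which pair of arms d refers to, whether the test is one- or two-sided, or whether alpha was adjusted for three comparisons. Section 3.1 lists two anxiety or stress measures, the VAS-A and the bracelet stress score. Neither is named as primary.

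**The concern.** The design and the analysis use different significance levels. If 32 per group gives 0.95 power for a pair at 0.05, it gives less at 0.0167, and the plan does not acknowledge the loss.

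The loss is also larger than it needs to be. Three groups are a special case: an omnibus gate can by itself control familywise error over the pairwise tests, so a correction behind the gate buys protection that is not needed at the 5% level.

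What is at stake is the chance of detecting a real VR effect. This matters most against the placebo-video arm, which watches the same video on a smartphone (section 3.2), so that this comparison isolates the headset.

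**Working it through.** **Inputs.** d = 0.920, alpha 0.05, power 0.95 and 32 per group (section 2.5); three arms (section 2.6); Kruskal-Wallis, then Bonferroni-corrected Mann-Whitney tests (section 5.4). Two-sided testing is assumed, because section 2.5 does not state sidedness.

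**1. Reproducing the 96.** For a two-sided two-sample t-test with n = 32 per group, the noncentrality is d·√(n/2) = 0.92 × √16 = 3.68 on 62 degrees of freedom. At alpha 0.05 power is 0.952, and 31 per group falls short of 0.95. So n = 32 and 32 × 3 = 96, an exact match. The alternatives tried do not match: a one-sided t-test needs 27 per group, a Mann-Whitney test (efficiency 3/π) needs 34, and a three-group ANOVA with f = d/2 = 0.46 needs 78 in total.

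**2. Power at the planned level.** The same calculation at 0.0167 gives:

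| Test, 32 per group, d = 0.92 | alpha 0.05 | alpha 0.0167 |
|---|---|---|
| t-test | 0.952 | 0.885 |
| Mann-Whitney, by efficiency 3/π | 0.943 | 0.867 |

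By t-test, 0.95 power at 0.0167 would need 41 per group, or 123 in total.

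**3. Why three arms are special.** Call the pairwise nulls (equal distributions) VR = video, VR = control and video = control. If any two hold, the third holds as well, so every intersection of two or more pairwise nulls is the global null. The closed family is therefore the global null plus the three pairwise nulls. A pair may be rejected at 0.05 once the global null has been rejected at 0.05, with strong familywise control. This fails with four or more arms.

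**4. Simulation.** 40,000 trials per scenario, 32 per arm, normal data; Kruskal-Wallis at 0.05, then Mann-Whitney tests.

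| Scenario | Quantity | Gate, then 0.0167 | Gate, then 0.05 |
|---|---|---|---|
| VR differs from both by 0.92 | power per comparison | 0.865 | 0.930 |
| | VR beats both | 0.780 | 0.898 |
| Same, rounded to 0–10 | power per comparison | 0.859 | 0.926 |
| | VR beats both | 0.772 | 0.891 |
| VR 0.92, video 0.46, control 0 (assumed) | VR vs video | 0.252 | 0.416 |
| | VR vs control | 0.860 | 0.889 |
| VR differs from both by 0.6 (assumed) | power per comparison | 0.45 | 0.57 |
| All arms equal | familywise error | 0.038 | 0.048 |
| One true null pair, third arm far off | familywise error | about 0.016 | about 0.05 |

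In the first scenario the gain is 0.930 − 0.865 = 0.065 per comparison and 0.898 − 0.780 = 0.118 for beating both. Bonferroni with no gate gives almost the same power there (0.865 per comparison, 0.780 for both), so the comparison does not depend on how the present plan is read.

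**5. What happens without the gate.** Three Mann-Whitney tests at 0.05 with no gate give a familywise error of about 0.12 when all arms are equal.

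**The case against.** - **The gate is not in the plan.** Section 5.4 lists two tests and only hints at a sequence. As written, Bonferroni may be the only familywise protection. This stands. It would be wrong to read the correction as simply redundant and delete it; it becomes dispensable only once the gate is a written rule.
- **The change is not free.** A reader might infer that the power comes at no cost in error. It does not: with one true null pair, error rises from about 1.6% to the nominal 5%. That is per outcome, and nothing in the plan corrects across VAS-A and bracelet stress. With VR shifted by 0.92 on both outcomes and an assumed correlation of 0 to 0.5, a false video–control claim on either outcome has a chance of about 3% as planned and 8.5–9% under the closed test. With all arms equal the figures are about 7.3% and 9–9.5%. This stands and shapes the fix.
- **The size depends on the scenario.** The gains of about 7 and 12 points need d = 0.92 against both comparators, which section 2.5 does not state. This stands. In the other scenarios run, the gain for a pair ranges from about 3 points (VR vs control, graded effect) to about 16 (VR vs video, graded effect).
- **Timing.** Sections 2.3 and 5.1 are in the past tense, with the study period ending on December 20, 2024. Loosening a threshold after seeing results would be post hoc. This stands.
- **Intervals.** A reader might also infer that section 5.5's "Confidence interval: 95" percent conflicts with tests at 0.0167. The plan attaches no interval to a pairwise difference, so the documents do not support that.
- **Kruskal-Wallis with Bonferroni is standard practice.** True, and it is valid. That does not restore the 0.95 power stated in section 2.5.

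**Conclusion.** The point holds as a mismatch between design and analysis, and as an avoidable loss of efficiency. It is not an error of inference. At d = 0.92 the planned pairwise tests have power of about 0.86 (0.885 by t-test), not 0.95. Closed testing with an explicit gate raises this to about 0.93 per comparison, which is still a little below 0.95. For VR beating both comparators, it raises power from 0.77–0.78 to about 0.89–0.90.

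The conclusion assumes two-sided tests, 32 evaluable patients per arm, roughly normal or rounded 0–10 data, and VR differing from both comparators by 0.92. The error control rests on exactly three arms, a written gate and nulls of equal distributions, and it applies to one outcome at a time.

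**What to change.** If no one has yet seen results by arm, replace the pairwise line in section 5.4 with:

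*If the Kruskal-Wallis test is significant at 0.05, each pairwise Mann-Whitney test is made at two-sided 0.05 (closed testing, three groups); if it is not, no pairwise difference is claimed.*

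In the same edit, name VAS-A or bracelet stress as primary, or limit the rule to one of them, because it does not cover multiplicity across the two.

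If results have been seen, keep the Bonferroni-corrected result as the main analysis and report the closed test as a labelled supplementary analysis. In section 2.5, restate the pairwise power as about 0.86–0.885 at the corrected level.

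The cost is a few sentences, with no extra patients, data or software. The statistical price is that error per outcome moves up to the nominal 5%.
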